5.2.2 Duration of treatment and criteria for retreatment

For patients receiving durvalumab + tremelimumab, retreatment is allowed (once only) for patients meeting the retreatment criteria below. The same treatment guidelines followed during the initial 12-month treatment period will be followed during the retreatment period, including the same dose and frequency of treatments and the same schedule of assessments. Radiotherapy is not required during retreatment, although it may be considered per the discretion of the treating physician.

Patients receiving the combination of durvalumab and tremelimumab may undergo retreatment in 2 clinical scenarios, described below:

1. Patients who achieve and maintain disease control (ie, CR, PR, or SD) through to the end of the 12-month treatment period may restart treatment with the combination upon evidence of PD, with or without confirmation according to RECIST 1.1, during follow-up.
2. Patients who complete the 4 dosing cycles of the combination of durvalumab and tremelimumab portion of the regimen (with clinical benefit per Investigator judgment), but subsequently have evidence of PD during the durvalumab monotherapy portion of the combination regimen, with or without confirmation according to RECIST 1.1, may restart treatment with the combination.
3. For the durvalumab + tremelimumab treatment group, before restarting their assigned treatment, the Investigator should ensure that the patient:

- a. Does not have any significant, unacceptable, or irreversible toxicities that indicate continuing treatment will not further benefit the patient
- b. Still fulfils the eligibility criteria for this study, including re-consenting to restart durvalumab and tremelimumab
- c. Has not have received an intervening systemic anticancer therapy after their assigned treatment discontinuation.
- d. Has had a baseline tumor assessment within 28 days of restarting their assigned treatment; all further scans should occur with the same frequency as during the initial 12 months of treatment (relative to the date of randomization) until study treatment is stopped (maximum of 13 cycles).

During the retreatment period, patients (> 30kg) receiving durvalumab + tremelimumab may resume durvalumab dosing at 1500 mg q4w with 75 mg of tremelimumab q4w for 4 doses each. Patients will then continue with durvalumab monotherapy at 1500 mg q4w, beginning at Week 16, for a total of 13 doses.

Treatment through progression is at the Investigator's discretion, and the Investigator should ensure that patients do not have any significant, unacceptable, or irreversible toxicities that indicate that continuing treatment will not further benefit the patient. A patient with a confirmed progression receiving durvalumab + tremelimumab cannot continue therapy or obtain retreatment if dosing is ongoing in the combination portion of therapy (q4w dosing).

Patients who AstraZeneca and/or the Investigator determine may not continue treatment will enter follow-up.

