Both durvalumab and tremelimumab have well established toxicity profiles as a single agent and in combination. However, the combination of durvalumab tremelimumab and palliative radiation has not been previously studied, this study will include a formal safety analysis in the first 6 patients accrued. Enrollment will be halted until these first 6 patients complete the first two cycles of treatment (8 weeks), and are evaluable for acute toxicities (toxicities reported within the 1st 8 weeks after treatment initiation). Specifically, if 2 or more DLTs (Refer to Section 6.4) are observed, then, durvalumab dosing will be modified to 1500 mg IV Q6 weeks x 9 doses and tremelimumab 75mg IV Q6 weeks x 3 doses for the remaining 14 patients (fixed dosing for patients > 30kg). If 1 or fewer DLTs are observed, then an additional 14 patients will be enrolled and treated at the initial dose and schedule of durvalumab and tremelimumab. Patients in the run in phase who experience DLTs will undergo dose modifications described in Appendix 1.

Toxicities will be graded based on CTCAE v. 4 and summarized as the number and percentage of patients with each type of toxicity. Responses will be summarized as frequencies and percentages. The Kaplan Meier method will be used to estimate overall survival and progression free survival. Outcomes will be calculated from the date of study entry to the date of the corresponding event.

We will use multivariate statistics to test the hypotheses that pretreatment intratumoral immune cell phenotype and PD-L1 expression predict response to therapy, and that therapy alters systemic immunophenotype.

Sample Size Determination:

There are multiple ongoing studies in various tumor types exploring the activity of durvalumab and tremelimumab. In a published report of the combination in patients with advanced NSCLC treated on a phase Ib study, Grade 3-4 toxicity was observed in 17% of patients. Similarly, in single institution reports of SBRT with the monoclonal antibody, grade 3 or higher toxicity was reported in 6-16% of patients. With a 20 patient accrual goal, toxicity rates can be estimated to within 22% with 95% confidence. Any toxicity with at least 10% prevalence has at least an 87% chance of being observed. This design allows us to reasonably exclude a clinically significant increase in toxicity with the addition of radiation therapy to the durvalumab and tremelimumab combination as defined by the upper bound of the confidence interval.

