19. Has a known history of Human Immunodeficiency Virus (HIV) (HIV 1/2 antibodies).
20. Has evidence of acute or chronic hepatitis B, or hepatitis C
21. Has received a live vaccine within 30 days prior to the first dose of trial treatment.
22. Has a Mean QT interval corrected for heart rate (QTc) ≥ 470 ms calculated from 3 electrocardiograms (ECGs) using Fredericia's Correction
23. Has a history of primary immunodeficiency or an allogeneic organ transplant
24. Has a history of hypersensitivity to durvalumab or tremelimumab excipient
25. Known history of previous clinical diagnosis of tuberculosis
26. Uncontrolled intercurrent illness including, but not limited to symptomatic congestive heart failure, uncontrolled hypertension, unstable angina pectoris, cardiac arrhythmia, active peptic ulcer disease or gastritis, seizures

Procedures for withdrawal of incorrectly enrolled patients are presented in Section 4.3. Withdrawn patients will not be replaced.

4.3 Withdrawal of Subjects from Study Treatment and/or Study Permanent discontinuation of durvalumab and or tremelimumab

An individual subject will not receive any further investigational product if any of the following occur in the subject in question:

- The subject or legal representative (such as a parent or legal guardian) withdraws consent.
- Confirmation of PD and investigator determination that the subject is no longer benefiting from treatment with durvalumab + tremelimumab
- Any AE that meets criteria for discontinuation as defined in Section 10.3.
- Adverse event that, in the opinion of the investigator or the sponsor, contraindicates further dosing
- Subject noncompliance that, in the opinion of the investigator or sponsor, warrants withdrawal; e.g., refusal to adhere to scheduled visits
- Subject is determined to have met one or more of the exclusion criteria for study participation at study entry and continuing investigational therapy might constitute a safety risk
- Intercurrent illness that prevents further administration of treatment
- Investigator's decision to withdraw the subject
- The subject has a confirmed positive serum pregnancy test
- Noncompliance with trial treatment or procedure requirements
- The subject is lost to follow-up
- Completed 13 cycles of durvalumab
- Grade ≥ 3 infusion reaction

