5.2 Dose and treatment regimens

5.2.1 Treatment regimens

Durvalumab + tremelimumab combination therapy

Patients (> 30kg in weight) will receive 1500 mg durvalumab via IV infusion q4w for up to 4 doses/cycles and 75 mg tremelimumab via IV infusion q4w for up to 4 doses/cycles, and then continue 1500 mg durvalumab q4w starting on Week 16 for a total of 13 doses. Dosing outside the window should be discussed with the Study Physician. Tremelimumab will be administered first. Durvalumab infusion will start 1 hour (+/- 5 mins.) after the end of tremelimumab infusion. The duration will be 1 hour(+/- 5 mins.) for each infusion. A 1 hour (+/- 5 mins.) observation period is required after the first infusion of durvalumab and tremelimumab. If no clinically significant infusion reactions are observed during or after the first cycle, subsequent infusion observation periods can be at the Investigator's discretion (suggested a minimum of 30 minutes after each durvalumab and tremelimumab infusion).

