6.2. Dosage and Administration

The treatment to be used in the run in phase of this trial for patients > 30kg is outlined in the Table below:

Drugs	Dose/Potency	Dose Frequency	Route of Administration	Regimen/Treatment Period
1. Durvalumab	1500 mg	Q4 weeks	IV infusion	Maximum of 13 doses
2. Tremelimumab	75mg	Q4 weeks	IV infusion	Maximum of 4 doses

If 2 or more DLTs (defined in Section 6.4) are observed in the run-in phase, the following treatment will be used for the remaining 14 patients to be treated on the clinical trial protocol:

Drugs	Dose/Potency	Dose Frequency	Route of Administration	Regimen/Treatment Period
1. Durvalumab	1500 mg	Q6 weeks	IV infusion	Maximum of 9 doses
2. Tremelimumab	75mg	Q6 weeks	IV infusion	Maximum of 3 doses

Patients who experience a DLT in the run in phase, will have dose interruptions/modifications as outlined in Appendix 1.

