8.3 Biological Sampling Procedures

8.3.1 Research Blood Collection

Blood will be collected for research purposes on three occasions: at baseline, prior to the second dose of durvalumab and tremelimumab and prior to the 4th dose of durvalumab and tremelimumab. Blood will be separated into cellular and serum components for preservation and batch analysis. Flow cytometric evaluation of CD3, CD4, CD8, CD14, PD-1, PD-L1, PD-L2 on peripheral blood mononuclear cells.

Specimen Requirements: Submission for flow cytometry

- A 5-10 mL specimen of peripheral blood in a lavender- (EDTA) or green- (sodium heparin) tube is acceptable for each draw.
- Storage/Transport Temperature: Specimens can be transported with a cold pack or wet ice, but do not fix or freeze specimens.
- Unacceptable Conditions: Frozen specimens, specimens greater than 48 hours old, specimens fixed in formalin for flow cytometry
- Address for shipping specimens:

Attn: [name], Hematopathology Lead

Seattle Cancer Care Alliance

Hematopathology Laboratory G7800

[name]

[name]

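### The retreatment rules in section 5.2.2 are written only for the 4-weekly schedule and contradict themselves for patients assigned to 6-weekly dosing after the run-in

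*Combined protocol and SAP*

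**What the plan says.** **The contingent schedule.** Section 6.2 sets the trigger: "If 2 or more DLTs (defined in Section 6.4) are observed in the run-in phase". The synopsis (Statistical Methods and Data Analysis) gives the consequence for the remaining 14 patients: "durvalumab dosing will be modified to 1500 mg IV Q6 weeks x 9 doses and tremelimumab 75mg IV Q6 weeks x 3 doses". The second table in 6.2 repeats 9 and 3 as maximum dose counts.

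**The initial schedule.** Section 5.2.1 describes 4-weekly dosing only: up to four combination cycles, "then continue 1500 mg durvalumab q4w starting on Week 16 for a total of 13 doses".

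**Retreatment.** Section 5.2.2 allows one retreatment.

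- Its opening paragraph carries the initial-period guidelines over, "including the same dose and frequency of treatments and the same schedule of assessments".
- Route 1 covers disease control to the end of the 12-month treatment period, followed by progression. It has no cycle count.
- Route 2 covers "Patients who complete the 4 dosing cycles of the combination of durvalumab and tremelimumab portion of the regimen", with clinical benefit, who then progress on durvalumab alone.
- Item d mentions a maximum of 13 cycles.
- The closing dosing paragraph says that retreated patients "may resume durvalumab dosing at 1500 mg q4w with 75 mg of tremelimumab q4w for 4 doses each", followed by durvalumab alone from Week 16 to a total of 13 doses.
- The next paragraph bars retreatment after confirmed progression during the combination portion, and labels that portion as q4w.

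Nothing in 5.2.2 mentions 6-weekly dosing.

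**Related wording.** Section 4.3 lists "Completed 13 cycles of durvalumab" among the reasons to stop. Section 8.1.3 treats stopping before 13 cycles as discontinuation. Section 8.3.1 places the third research blood draw "prior to the 4th dose of durvalumab and tremelimumab".

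**The concern.** The 6-weekly schedule is a branch that the protocol itself plans for, and it would cover most of the trial. A patient on that branch who progresses and is considered for retreatment meets a section that answers the same question in two ways. The opening sentence points to the schedule the patient was on. The closing paragraph, taken alone, points to the schedule that was replaced for this cohort because of DLTs. Route 2 asks for a cycle count that this cohort's own cap rules out.

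At stake is consistent conduct. Investigators could reasonably choose differently between the two instructions, and two patients in the same position could be handled differently. Safety is the primary endpoint. Section 11.2.1 assesses all enrolled patients and does not separate first-course from retreatment events. The stopping rule in 3.3 counts Grade 4 or higher drug-related toxicity throughout the trial. The schedule on which a retreatment event occurred would therefore matter when the safety results are read.

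**Working it through.** **1. The plan's own figure.** Monotherapy start = dosing interval x number of combination doses. On the initial schedule, 4 weeks x 4 doses = Week 16. This reproduces the week given in 5.2.1 and 5.2.2.

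**2. The same arithmetic on the modified schedule.** Inputs are the counts and intervals in the synopsis and 6.2. I assume both drugs start at Week 0 and are given together until tremelimumab ends.

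| | Initial schedule | Modified schedule (6.2) | 5.2.2 closing paragraph |
|---|---|---|---|
| Interval (weeks) | 4 | 6 | 4 |
| Tremelimumab doses | 4 | 3 | 4 |
| Combination weeks | 0, 4, 8, 12 | 0, 6, 12 | 0, 4, 8, 12 |
| Monotherapy start | 4 x 4 = Week 16 | 6 x 3 = Week 18 | Week 16 |
| Durvalumab doses | 13 | 9 | 13 |
| Last durvalumab dose | 12 x 4 = Week 48 | 8 x 6 = Week 48 | Week 48 |
| Tremelimumab total | 4 x 75 = 300 mg | 3 x 75 = 225 mg | 300 mg |
| Durvalumab total | 13 x 1500 = 19,500 mg | 9 x 1500 = 13,500 mg | 19,500 mg |

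The closing paragraph matches the initial schedule in every row. It matches the modified schedule only in the week of the last dose. Relative to the modified schedule, it gives 300/225 = 1.33 times the tremelimumab, 19,500/13,500 = 1.44 times the durvalumab, and 6/4 = 1.5 times the dosing frequency.

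**3. The entry routes.** Route 2 needs 4 combination cycles and the modified schedule allows 3, so it cannot literally be met. Route 1 needs disease control through the 12-month period. Both schedules place the last dose at Week 48, so route 1 remains open.

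**4. How likely the branch is.** The protocol states no expected DLT rate. For an assumed rate p, with six independent patients:

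P(2 or more of 6) = 1 - (1-p)^6 - 6p(1-p)^5

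- p = 0.10: 1 - 0.5314 - 0.3543 = 0.114
- p = 0.17: 1 - 0.3269 - 0.4018 = 0.271
- p = 0.30: 1 - 0.1176 - 0.3025 = 0.580

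The 17% is the Grade 3-4 toxicity rate cited in 11.3 for the drug combination in lung cancer. It is only a proxy: section 6.4 limits DLTs to 28 days and lists exclusions. The 10% and 30% are there to show the range.

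**5. How many patients.** The modified cohort is 14 of 20 (70%). Retreatment further requires prior disease control or clinical benefit, later progression, no intervening systemic therapy, continuing eligibility and re-consent. The documents give no retreatment rate, so 14 is a ceiling.

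**The case against.** The strongest reply is that section 5 simply describes the base schedule, and that 6.2 overrides it when the trigger is met. On that view the opening sentence of 5.2.2, and its later reference to restarting the assigned treatment, both lead a 6-weekly patient back to 6-weekly dosing. The q4w sentence is also permissive. This is a fair reading and may be what was meant. However, 6.2 does not mention retreatment, and the closing paragraph of 5.2.2 gives explicit numbers without limiting them to one cohort. The conflict stays on the page.

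A second reply is that literal reading proves too much. Retreated patients must still meet the eligibility criteria, and exclusion 18 bars prior anti-CTLA-4 therapy, so strictly nobody who has had tremelimumab could be retreated. This shows that the text alone cannot predict what investigators would do. It does not reconcile the two dosing instructions.

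Several replies stand and limit the point:

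- Sections 6.2 and the synopsis change the schedule only for the remaining 14 patients. Nothing moves run-in patients without a DLT off 4-weekly dosing, so the protocol does not reject that schedule for everyone.
- The 13-cycle item in 4.3 is one of several stopping conditions. Section 6.2 separately caps the modified schedule at 9 doses, so 4.3 does not authorise further dosing.
- Section 3.2 and footnote j of the Schedule of Study Assessments tie the third blood draw to cycle 4. If a cycle follows each durvalumab dose, cycle 4 exists on 6-weekly dosing (Week 18, durvalumab alone). Only 8.3.1 refers to a fourth dose of both drugs.

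**Conclusion.** The point holds as a conditional inconsistency in a dosing rule. For patients on the modified schedule, 5.2.2 contradicts itself on the retreatment regimen, sets a route 2 condition that they cannot literally meet, and labels the combination portion with an interval that is not theirs. Read alone, the closing paragraph could return a patient who enters by route 1 to the replaced schedule. The opening sentence permits retreatment on the modified schedule instead.

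Three stronger inferences are not supported:

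- A reader might infer that these patients must either go without retreatment or be returned to 4-weekly dosing. Route 1, the opening sentence and the permissive wording leave a third possibility.
- A reader might infer that 70% of the trial is affected. That is the whole cohort; only those who reach retreatment are affected, and their number is unknown.
- A reader might infer that the primary safety result would become uninterpretable. No section labels safety results by schedule, and section 10.3 collects adverse event start and stop dates, so events after retreatment can be identified.

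The size therefore rests on two unknowns: the true DLT rate (branch probability 11% to 58% over assumed rates of 10% to 30%) and the fraction retreated. The correction should be made because the conflict concerns dosing after DLTs and is cheap to remove. No view is taken here on which schedule or rule is right.

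**What to change.** Reconcile 5.2.2 with the modified schedule in 6.2. Four places need it: the cycle count in route 2, the 13-cycle maximum in item d, the closing dosing paragraph, and the q4w label in the paragraph on treatment through progression. Replace fixed intervals, counts and weeks with wording tied to the cohort's assigned schedule, and state what retreatment, if any, applies to patients on the modified schedule. The sponsor decides the clinical content.

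Minor conforming edits:

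- Align the 13-cycle wording in 4.3 and 8.1.3 with the 9-dose cap. As written, 8.1.3 would literally class a patient who completed all 9 planned doses as having stopped early.
- Align the third blood draw in 8.3.1 with the cycle 4 wording in 3.2 and footnote j of the assessment schedule.

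Optionally, tabulate adverse events after the start of retreatment separately, using the dates already collected. This helps interpretation but is not needed to remove the contradiction.

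The cost is one wording amendment, submitted for approval as section 12.4 requires. It needs no extra patients, visits or samples.

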3. STUDY DESIGN

3.1 Overview of study design

This study will be carried out as a single institution, single arm phase I/II unblinded trial. A maximum of 20 patients will be enrolled. Each patient will be treated with durvalumab, tremelimumab and palliative hypofractionated radiation therapy using either HIGRT or SBRT. Durvalumab will be continued for 13

cycles, unless evidence of unacceptable toxicity, disease progression or withdrawal of patient consent were to occur.

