3.2 Study Schema

The first 6 patients of this study will represent the initial run-in phase of the triplet combination of durvalumab, tremelimumab and HIGRTor SBRT. Fixed doses of Durvalumab and Tremelimumab will be administered on day 1 of therapy. Radiation will be initiated on Week 3 of the 28 day cycle. Radiation will be delivered to a total dose of 24 Gy, given in 3 fractions of 8Gy every other day. Durvalumab will be continued for a total of 13 cycles, and tremelimumab for a total of 4 cycles unless patient withdraws consent, has confirmed disease progression, and/or develops toxicity that results in treatment discontinuation.

Serum correlative studies will be collected at the following timepoints: at baseline, prior to cycle #2, and prior to cycle#4 of treatment. Archived formalin fixed paraffin embedded tissue will be collected from patients enrolled. If the patient does not have archived tissue available, a fresh biopsy will be obtained.

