9. DISEASE EVALUATION AND METHODS

The response to immunotherapy may differ from the typical responses observed with cytotoxic chemotherapy including the following (Wolchok et al 2009, Nishino et al 2013):

- Response to immunotherapy may be delayed
- Response to immunotherapy may occur after PD by conventional criteria
- The appearance of new lesions may not represent PD with immunotherapy
- SD while on immunotherapy may be durable and represent clinical benefit.

Based on the above-described unique response to immunotherapy and based on guidelines from regulatory agencies, e.g., European Medicines Agency's "Guideline on the evaluation of anti-cancer medicinal products in man" (EMA/CHMP/205/95/Rev.4) for immune modulating anti-cancer compounds, the study may wish to implement the following in addition to standard RECIST 1.1 criteria:

- RECIST will be modified so that PD must be confirmed at the next scheduled visit, preferably, and no earlier than 4 weeks after the initial assessment of PD in the absence of clinically significant deterioration. Treatment with durvalumab + tremelimumab would continue between the initial assessment of progression and confirmation for progression.
- In addition, subjects may continue to receive durvalumab + tremelimumab beyond confirmed PD in the absence of clinically significant deterioration and if investigators consider that subjects continue to receive benefit from treatment.

Modification of RECIST as described may discourage the early discontinuation of durvalumab + tremelimumab and provide a more complete evaluation of its anti-tumor activity than would be seen with conventional response criteria. Nonetheless, the efficacy analysis will be conducted by programmatically deriving each efficacy endpoint based on RECIST 1.1 criteria.

Of note, clinically significant deterioration is considered to be a rapid tumor progression that necessitates treatment with anti-cancer therapy other than durvalumab + tremelimumab or with symptomatic progression that requires urgent medical intervention (e.g., central nervous system metastasis, respiratory failure due to tumor compression, spinal cord compression).>>

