Appendix 3**Schedule of study procedures: follow-up for subjects who have discontinue durvalumab and tremelimumab treatment due to confirmed progression of disease at the investigator discretion**

Evaluation	Time Since Last Dose of MEDI4736							12 Months and Every 6 Months (±2 weeks)	
	Day (±3)	Months (±1 week)							
	30	2	3	4	6	8	10		
Physical examination	X								
Vital signs (temperature, respiratory rate, blood pressure, pulse)	X								
Weight	X								
AE/SAE assessment	X	X	X						
ECOG performance status	X	X	X						
Survival status: phone contact with subjects who refuse to return for evaluations and agree to be contacted		X	X	X	X	X	X	X (every 2 months)	
Hematology	X								
Serum chemistry	X								
Tumour assessment (CT or MRI)		For subjects who continue on MEDI4736 post-confirmed progression at the investigator's discretion (following consultation with the sponsor), tumour assessments should be performed relative to the date of first infusion until MEDI4736 is stopped. For subjects who discontinue MEDI4736 following confirmed progression , scans should be conducted according to local clinical practice.

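### The protocol contradicts itself on dosing after confirmed progression, so the last dose that sets the adverse event and Grade 4+ stopping-rule windows depends on which section is followed

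*Combined protocol and SAP*

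**What the plan says.** Six places in the protocol bear on dosing after progression.

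- **Section 3.1** continues durvalumab for 13 cycles "unless evidence of unacceptable toxicity, disease progression or withdrawal of patient consent were to occur". It does not mention confirmation.
- **Section 3.2** continues both drugs for their planned cycles "unless patient withdraws consent, has confirmed disease progression, and/or develops toxicity that results in treatment discontinuation". It leaves no discretion.
- **Section 4.3** lists, among the events that end study drug, "Confirmation of PD and investigator determination that the subject is no longer benefiting from treatment with durvalumab + tremelimumab". Both conditions must be met, and no phase is singled out.
- **Section 5.2.2** begins generally: "Treatment through progression is at the Investigator's discretion". It then sets a limit: "A patient with a confirmed progression receiving durvalumab + tremelimumab cannot continue therapy or obtain retreatment if dosing is ongoing in the combination portion".
- **Section 9** is introduced with "the study may wish to implement the following in addition to standard RECIST 1.1 criteria". It goes on to say that "subjects may continue to receive durvalumab + tremelimumab beyond confirmed PD in the absence of clinically significant deterioration", if the investigator considers that there is still benefit. It neither excepts the combination phase nor refers to Section 5.2.2.
- **Appendix 3** has a tumour-assessment entry that opens "For subjects who continue on MEDI4736 post-confirmed progression at the" investigator's discretion, and adds consultation with the sponsor.

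Safety and tolerability is the primary endpoint, assessed in all enrolled patients (Section 11.2.1). Adverse events are recorded until 90 days after the last dose (Section 10.3.1). The Grade 4+ rule that halts enrolment counts events up to 30 days after the last infusion (Section 3.3).

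**The concern.** For a patient whose progression is confirmed while both drugs are being given, Sections 5.2.2 and 3.2 end treatment, while Section 9 lets it go on. Two investigators could treat the same patient differently and each cite the protocol.

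This is first a safety matter, because it decides whether a patient receives further doses. It also reaches the safety analysis. The 90-day and 30-day windows are both anchored on the last dose, so the rule applied determines how much exposure and observation time that patient contributes to the toxicity summary, and whether a late Grade 4+ event counts toward halting enrolment. With 20 patients, each one is 1/20 = 5 percentage points of any toxicity rate.

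**Working it through.** **1. The plan's own figures.** With n = 20 and a rate of 0.5, the 95% half-width is 1.96 × √(0.25/20) = 0.219, against the stated 22%. The chance of seeing a 10% toxicity at least once is 1 − 0.9^20 = 0.878, against at least 87%. The chance of three or more events is 0.794 (n = 20, rate 20%), 0.909 (n = 20, rate 25%) and 0.833 (n = 10, rate 40%), against 80%, 91% and 83%. All reproduce. They depend only on the number of patients and the assumed rates, so no dosing rule changes them.

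**2. The rules side by side, once progression is confirmed.**

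| Place | During combination dosing | During durvalumab alone |
|---|---|---|
| 3.1 | durvalumab stops (even without confirmation) | durvalumab stops |
| 3.2 | both drugs stop | durvalumab stops |
| 4.3 | a trigger only if benefit is also lost | same |
| 5.2.2 | stops, no retreatment | investigator's discretion |
| 9 (optional wording) | may continue | may continue |
| Appendix 3 | continued dosing foreseen, after sponsor consultation; phase not stated | same |

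The main conflict is in the middle column: 5.2.2 and 3.2 against 9. In the right-hand column, 3.1 and 3.2 also conflict with 5.2.2, 9 and Appendix 3.

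**3. Dose calendar.** Inputs: durvalumab every 4 weeks for 13 doses, so weeks 0, 4, ..., 48; tremelimumab at weeks 0, 4, 8 and 12; durvalumab alone from week 16 (Section 5.2.1); scans every 8 ± 1 weeks (schedule of assessments); confirmation preferably at the next scheduled visit and at least 4 weeks after first progression (Section 9). A result is taken to be known before any dose due the same week.

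- First scan at week 7-8, earliest confirmation at 7 + 4 = 11 to 8 + 4 = 12. Three doses of each drug have been given. In dispute: tremelimumab 4 − 3 = 1, durvalumab 13 − 3 = 10.
- First scan at week 9, earliest confirmation at week 13. Four doses of each have been given. In dispute: tremelimumab 0, durvalumab 13 − 4 = 9.
- Confirmation at the next scheduled scan, week 15-16. Four doses of each have been given. In dispute: tremelimumab 0, durvalumab 9, provided that the combination portion is read as lasting until week 16.

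Section 5.2.2 does not settle where that portion ends. It labels it by four-weekly dosing, but durvalumab alone is also four-weekly, and the modified combination schedule in Section 6.2 is six-weekly. On the six-weekly schedule (durvalumab at weeks 0, 6, ..., 48; tremelimumab at weeks 0, 6 and 12), confirmation at week 11-12 leaves one tremelimumab and seven durvalumab doses in dispute.

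**4. Windows on the four-weekly schedule.** The last dose is at week 8 or 12 under one reading and as late as week 48 under the other, a shift of 48 − 12 = 36 to 48 − 8 = 40 weeks. For a last dose at week 8 or week 48:

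- The 90-day window ends at 8 + 90/7 ≈ week 21 or 48 + 90/7 ≈ week 61.
- The 30-day window ends at 8 + 30/7 ≈ week 12 or 48 + 30/7 ≈ week 52.

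**5. Run-in decision.** Section 6.4 gives a 28-day DLT period; Section 3.3 and the synopsis give 8 weeks. On scheduled scans, confirmation cannot come before about week 11, after both.

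**6. Illustration only.** The documents give no toxicity rate by exposure. Assume a 20% Grade 4+ rate, with 5 to 10 points more in patients who continue, and 2 to 10 of the 20 continuing. The expected overall rate runs from (18 × 0.20 + 2 × 0.25)/20 = 20.5% to (10 × 0.20 + 10 × 0.30)/20 = 25%. The chance of three or more events runs from 81% to 91%, against 79% if nobody continues.

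**The case against.** The strongest reply is that the text can be read in harmony. Section 9 gives an optional, general permission; Section 5.2.2 gives the same general discretion and carves out one specific exception. Section 4.3 lists events that are each sufficient to stop and never says that a patient must otherwise continue, so an added bar in 5.2.2 is compatible with it. The two drug names joined by a plus sign also serve as the regimen's name (Section 10.3.1 uses them that way), so Section 9 need not mean the combination phase. Section 3.1 is an overview sentence.

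Much of this stands. A reader might infer several mutually exclusive rules; the documents do not show that, because 4.3 is compatible with 5.2.2 and the Section 9 text may not be in force. A reader might also take week 12 as the typical time of confirmation. It is only the earliest for a first scan at week 8; the preferred next visit, if it is the next scan, puts it near week 16, when tremelimumab is complete and the 5.2.2 bar may no longer apply.

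It does not remove the conflict. Neither Section 9 nor 4.3 points to the exception. Section 3.2 ends both drugs at confirmed progression without qualification, which disagrees with Section 9 in either phase and with 5.2.2's own discretion during durvalumab alone. Optional wording leaves unanswered whether the permission applies, which is itself a reason to settle it.

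**Conclusion.** The contradiction is real and should be resolved. In the first four-weekly course it concerns at most one tremelimumab dose and about 9-10 durvalumab doses per patient progressing at the first scan, and up to about 40 weeks in the last dose that anchors the two safety windows. These are ceilings. They assume no dose delays, scheduled scans only, and a patient who remains free of clinically significant deterioration, with investigator-judged benefit, until week 48. The documents give no frequency for such patients.

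A reader might go further and infer that this conflict is why exposure behind the primary toxicity rate is not fixed, or that the safety design fails. The documents do not support either. Exposure varies under any single rule through toxicity stops, investigator withdrawal and the optional retreatment course; this is one avoidable source among several. The run-in DLT decision and the stated precision and detection figures are untouched. The Grade 4+ rule is affected only through its window, and only while enrolment is open. Section 9 derives efficacy endpoints from RECIST 1.1, so the definitions of response and PFS do not depend on which rule applies. The documents offer no basis for sizing an effect on overall survival.

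**What to change.** Reconcile Sections 3.1, 3.2, 4.3, 5.2.2 and 9 and Appendix 3 into one rule on dosing after progression, stated once and cited in the other places. It should say:

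- whether progression must be confirmed before the rule applies;
- whether the optional Section 9 text is in force in this study;
- where the combination portion ends, on both the four-weekly and the six-weekly schedule;
- whether consultation with the sponsor is a condition.

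This review takes no view on which rule is right.

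A descriptive toxicity table is optional. If one is added, split it at confirmed progression rather than first progression, because Section 9 has dosing continue between the two and the disputed doses come after confirmation. Section 10.3 already collects adverse event start and stop dates, so the table needs no new safety data. The cost is amendment wording and, at most, one table. The sample size does not change.
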